11.8.5 Overall Survival

Overall survival (OS) is defined as the number of days from Day 1 of Cycle 1 to death due to any cause. If a subject is not known to have died, then OS will be censored at the latest date the subject was known to be alive (on or before the cut-off date)

11.8.6 Minimal Residual Disease

The rate of MRD-negativity is defined as the proportion of patients with at least 1 MRD-negative sample. Duration of MRD-negativity is defined as the number of days from the first documentation of MRD-negativity to the date of MRD status change (not MRD-negativity).

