Visit Window			+2d	+2d	+2d	±4d	+7d		
Predose (-30 min)	9.5, 9.6	ADA/PK: 09 and 13	PK: 09 and 13	PK: 09 and 13	PK: 09 and 13	ADA ^c /PK: 09 and 13	ADA ^c		
Start of GEN3013 injection +1 hour (+15 min)									
End of GEN3009 Infusion +5 min ^a (+5 min)		PK: 09 only							
Unscheduled Visit								PK: 09 and 13	PK: 09 and 13

Note: Sample collection timing may be modified during the trial based on emerging data.

09=GEN3009; 13=GEN3013.

- a. After flush.
- b. Only in case of full infusion on Day 1.
- c. Only in case of split dose between Day 1 and Day 2.
- d. In case of split dose between Day 1 and Day 2, the Day 4 sample will be 48 hours after the complete infusion.
- e. Even cycles only.

Table 13 Visit Assessment Schedule for Biomarkers – Expansion GEN3009 + GEN3013 (including Safety Run-in)

Treatment Cycle: 28-day cycle	Section	Cycles 1 and 2										
		Screening	1d	2d	2d+2h	4d	8d	15d	16d	22d	22d+6h	23d
Visit Window							+2d	+2d		+2d	+8h	
Tumor Biopsy	9.7/ 9.8.2	X ^a	X ^{b,f}									
Cytokines	9.8.3.2		X ^c				X ^{c,d}	X ^{d,h}		X ^{c,d}	X ^d	X ^d
Complement	9.8.3.3		X ^c	X ^{d,i}	X ^{d,j}			X ^{c,d}	X ^d			
Immunophenotyping	9.8.3.1		X ^c	X ^{d,i}		X ^{d,j}	X ^{c,d}	X ^c		X ^{c,d}	X ^d	
PBMC	9.8.3.1		X ^c				X ^{c,d}	X ^{c,d}		X ^c		
Saliva DNA	9.8.3.4	X										
ctDNA/MRD Plasma	9.8.3.4/ 9.2.2.3		X ^c									

Treatment Cycle	Section	Cycle 3		Cycles 4-12	Unscheduled	Treatment Discontinuation Visit
		1d	15d	1d		
Day			+2d	±4d		
Visit Window						
Tumor Biopsy	9.7 /9.8.2					X ^b
Cytokine	9.8.3.2	X ^c			X	
Complement	9.8.3.3			X ^{c,e}	X	X
Immunophenotyping	9.8.3.1	X ^c	X ^c	X ^{c,e}	X	
PBMC	9.8.3.1			X ^{c,e}	X	X
Saliva DNA	9.8.3.4					

ctDNA/MRD Plasma	9.8.3.4/ 9.2.2.3	X ^c		X ^{c,g}	X	
---------------------	---------------------	----------------	--	------------------	---	--

a. Fresh lymph node biopsy (to be taken from patients with easily accessible lesions) or an archival lymph node biopsy (formalin-fixed paraffin-embedded, which is taken after most recent therapy prior to enrollment and taken within 6 months of Cycle 1 Day 1) is mandatory for lymphoma.

b. Unless otherwise agreed with sponsor's medical monitor or delegate, a fresh core biopsy is to be taken from patients with easily accessible lesions in Cycle 2 and at the End of Treatment visit.

c. If the visit occurs on an infusion day, the sample must be taken before IMP treatment(s) (-30 minutes).

d. Cycle 1 only.

e. Samples in even cycles only, starting Cycle 4.

f. Cycle 2 only.

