g. Samples to be taken C5, C7, C10 and C13 only. After C13 a sample will be obtained every 6 months (± 1 month) for up to 3 years.

h. Sample to be taken during Safety Run-in only.

i. Only in case of full infusion of GEN3009 on Day 1

j. Only in case of GEN3009 split dose between Day 1 and Day 2

Table 14 Visit Assessment Schedule for MRD – Expansion GEN3009 + GEN3013

Cycle	Cycles 1, 2, 3, 5, 7, and 10	Cycle 13 and onward
Day or Time post dose (window)	Day 1 (+2 days)	Day 1 (+2 days)
Whole blood MRD ^a	X	A whole blood sample will be obtained every 6 months (± 1 month) for up to 3 years
Bone marrow aspirate MRD	
For B-cell NHL subjects with bone marrow involvement at baseline: If a subject is in CR by FDG-PET, a portion of the aspirate collected to confirm CR will be used to assess MRD.For B-cell NHL subjects with no bone marrow involvement at baseline, no bone marrow examination for MRD is required.If a subject is MRD-positive in the bone marrow but maintains CR, an additional bone marrow aspirate will be collected after 3 months, if clinically feasible.	

a. Upon reaching CR on PET-CT scan, an additional blood sample will be collected if not within 2 weeks of another collection to evaluate MRD.

Table 15 GEN3013 Repriming Cycle – Expansion GEN3009 + GEN3013 (including Safety Run-in)

	Day 1	Day 8	Day 15	Day 22
Body Weight	X		X	
Complete physical examination	X			
Lymph node examination	X			
Neurological Evaluation (ICANS) ^b	X	X	X	X
Vital signs ^c	X	X	X	X
12-Lead ECG (triplicate)	X			
ECOG Performance Status	X			
Constitutional Symptoms (ie, B Symptoms)	X		X	
Adverse Events	X	X	X	X
Previous and concomitant medications	X	X	X	X
Concomitant procedures	X	X	X	X
STUDY TREATMENT ADMINISTRATION				
Hospitalization ^d			X	
Premedications ^e	X	X	X	X
CRS prophylaxis ^f	X	X	X	X
GEN3013 administration	X	X	X	X
LOCAL LABORATORY ASSESSMENTS				
Hematology	X		X	
Biochemistry	X		X	
Coagulation	X		X	
Immunoglobulins (IgA, IgE, IgG, gM)	X			
Urinalysis	X			
Pregnancy Test (urine or serum) ^g	X			
TLS Monitoring			X	
CENTRAL LABORATORY ASSESSMENTS				
Immunophenotyping (by flow cytometry)	X ^h	X ^h	X ^h	X
Pharmacokinetics (GEN3009 and GEN3013)	X ^h	X ^{h,i}	X ^{h,i}	X ^{h,i}
Anti-drug antibodies	X ^h			

- a. Once the full repriming cycle is completed, the subject should resume treatment with Day 1 of the next planned cycle (subsequent to the cycle during which the dosing was delayed); see Section 7.4.2.2.

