
Assess pharmacodynamic markers related to MoA of GEN3009 and GEN3013	
Pharmacodynamic markers in blood samples (leukocyte subset frequencies and phenotype, target antigen expression, complement regulatory protein expression, plasma complement levels and activation [CH50], and cytokine levels)

Table 20 Objectives and Endpoints for Expansion (GEN3009 + GEN3013 for R/R DLBCL)

OBJECTIVES	ENDPOINTS
Primary	
• Assess preliminary anti-tumor activity of GEN3009 + GEN3013 combination	• CR rate
Secondary	
• Further assess the preliminary anti-tumor activity of GEN3009 + GEN3013 combination	• ORR • DOR • TTR • PFS • OS • Rate and duration of MRD negativity
• Evaluate the safety and tolerability of GEN3009 + GEN3013	• Frequency and severity of AEs/AESIs/SAEs • Changes in laboratory parameters • Changes in vital signs • Frequency of dose interruptions, dose delays, and dose intensity
• Establish the PK properties of GEN3009 and GEN3013	• PK parameters: CL, AUC _{7days} , AUC _{last} , C _{max} , T _{max} , C _{trough} , and T _{1/2}
• Evaluate immunogenicity	• Incidence of neutralizing ADAs to GEN3009 • Incidence of neutralizing ADAs to GEN3013
Exploratory	
• Assess potential biomarkers predictive of clinical response to GEN3009 + GEN3013 combination	• Expression of CD3, CD20, CD37, and other markers in tumor biopsies before and during treatment • DNA mutation status and gene expression profiling (RNA-seq) in blood and malignant cells • ctDNA as response biomarker • Evaluation of immune populations, phenotype and function in tumors and blood
• Assess pharmacodynamic markers linked to efficacy and MoA of GEN3009 and GEN3013	• Pharmacodynamic markers in blood samples and within tumor (on-treatment biopsy) ((leukocyte subset frequencies and phenotype, target antigen expression, complement regulatory protein expression, plasma complement levels and activation (CH50), cytokine levels)

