5.2.2 Expansion (including Safety Run-in) Exclusion Criteria

Any potential subject who meets any of the following criteria will be excluded from participating in the trial.

1. Prior treatment with a CD37-targeting agent.
2. **GEN3009 + GEN3013 combination cohort only:** Prior treatment with a CD3 × CD20 bispecific antibody.
3. Prior allogeneic HSCT.
4. Autologous HSCT within 3 months before the first dose of GEN3009.
5. Lymphomas leukemia phase: high absolute lymphocyte count or the presence of abnormal cells in the peripheral blood indicating circulating lymphoma cells

6. Treatment with an anti-cancer biologic including anti-CD20 therapy, radio-conjugated or toxin-conjugated antibody or CAR T cell therapy within 4 weeks or 5 half-lives, whichever is shorter, before the first dose of GEN3009. Treatment with small molecules such as BTK inhibitors, BCL2 inhibitors, or PI3K inhibitors within 5 half-lives prior to the first dose of GEN3009.
7. Chemotherapy or radiation therapy within 2 weeks of the first dose of GEN3009.
8. Treatment with an investigational drug or an invasive investigational medical device within 4 weeks or 5 half-lives, whichever is shorter, prior to the first dose of GEN3009, and at any time during the study treatment period
9. Autoimmune disease or other diseases that require permanent or high-dose immunosuppressive therapy.
10. Received a cumulative dose of corticosteroids more than the equivalent of 250 mg of prednisone within the 2-week period before the first dose of GEN3009.

Note: Refer to Section [6.6.1](#) for steroid dosing limitations during the study treatment period.

11. Has uncontrolled intercurrent illness, including but not limited to:
 - a. Ongoing or active infection requiring intravenous antibiotics treatment at the time of enrollment or within the previous 2 weeks prior to the first dose of GEN3009 or GEN3013
 - b. Symptomatic congestive heart failure (grade III or IV as classified by the NYHA), unstable angina pectoris or cardiac arrhythmia (refer to [Appendix 2](#)) and/or known decrease ejection fraction of <45%
 - c. Myocardial infarction, intracranial bleed, or stroke within the past 6 months
 - d. Screening 12-lead ECG showing a baseline QTcF >480 msec
12. **GEN3009 + GEN3013 combination cohort only:** Seizure disorder requiring therapy (such as steroids or anti-epileptics)
13. History of severe allergic or anaphylactic reactions to monoclonal antibody therapy.

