5.2.4 Minimal residual disease (MRD) determination

The level of minimum residual disease (MRD) will be assessed based on results from B-cell receptor (BCR) sequencing at timing of the radiological assessments. The level of MRD may conceptually be classified as “negative” (if MRD level is below a cut-off) or “positive” (if MRD level is above a cut-off). Three cut-offs may be used to classify the level of MRD: 10^{-4} , 10^{-5} , and 10^{-6} , where 10^{-5} is considered as the primary cut-off, and the others may be used for sensitivity analysis.

Given a cut-off, the “overall MRD status” is defined as:

- “MRD negative (cut-off)” as having at least one MRD negative result while on treatment (may or may not have indeterminate result)
- “MRD positive (cut-off)” as lacking an MRD negative result while on treatment (subjects who are continuously MRD positive, MRD indeterminant, not tested, or missing MRD samples throughout trial)

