- The pre-treatment period includes information collected from the date of informed consent until the day prior to the first dose of trial medication. (Subjects not receiving trial medication will remain in the pre-treatment period for the duration of their participation.)
- The on-treatment period begins on the date of the first dose of trial medication, and stops 4 weeks (i.e. 28 days) after last dose of trial medication.
- The post-treatment period begins at end of on-treatment period + 1 day

If incomplete data makes it impossible to definitively assign an observation to one of these periods, the data will be conservatively assigned to the on-treatment period.

Definition of analysis time points or time windows

Data reported on the CRF will be assigned to analysis visits as follows, where 'visit' refers to visit name or cycle day, as applicable. Data will be listed by nominal visit, as recorded on the CRF, and summarized in tables and figures using the analysis day:

- a) Visits prior to the date of first dose of trial medication will be assigned to the Screening visit.
- b) Scheduled post-baseline visits other than end of treatment or end of trial visits will be assigned to the nominal visit.
- c) Regularly scheduled assessments occurring at an unscheduled visit, end of treatment visit, or end of trial visit will be assigned to the closest scheduled visit (or the later of the two visits, if equidistant between scheduled visits). For example, if a subject completes Cycle 3 Day 8 visit and returns 2 days later for an end of treatment visit, the assessments collected at that visit would be assigned to Cycle 3 Day 11.
- d) If >1 assessment of a certain type is assigned to a given analysis visit:
 - i. If only 1 assessment is non-missing, the non-missing results will be summarized.
 - ii. If >1 assessment is non-missing, and only 1 assessment is within the visit window, the assessment within the visit window would be summarized.
 - iii. If >1 non-missing assessments are within the visit window, and one was collected at the actual visit, that assessment will be used. Otherwise, the one that is closest to the planned time of the visit will be used.

5.9 *Multiple Comparison/Multiplicity*

No multiplicity adjustment is planned.

6 Subject Accounting and Disposition

6.1 *Subject accounting*

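### The MRD-negativity rate counts any one negative sample and does not require detectable MRD at baseline, so a subject never positive in blood can score as a success with no drug effect

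*Protocol*

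**What the plan says.** Table 20 of the protocol lists "Rate and duration of MRD negativity" among the secondary endpoints of the GEN3009 + GEN3013 cohort in R/R DLBCL (n=20). In Tables 17 to 19 MRD status is exploratory only.

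Section 11.8.6 gives the scoring rule: "The rate of MRD-negativity is defined as the proportion of patients with at least 1 MRD-negative sample". For the time component it says: "Duration of MRD-negativity is defined as the number of days from the first documentation of MRD-negativity to the date of MRD status change". Neither sentence mentions when the sample was taken relative to dosing, a positive baseline, a trackable clone, a cut-off, or whether the sample is blood or marrow.

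Table 14 schedules whole-blood MRD on Day 1, with a window of +2 days, of "Cycles 1, 2, 3, 5, 7, and 10". It does not say that the Cycle 1 sample is pre-dose. Table 13 schedules a separate ctDNA/MRD plasma sample on Cycle 1 Day 1, and its footnote c requires that sample before dosing.

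Expansion exclusion 5 (section 5.2.2) removes: "Lymphomas leukemia phase: high absolute lymphocyte count or the presence of abnormal cells in the peripheral blood indicating circulating lymphoma cells".

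SAP 5.2.4 classes a subject as MRD negative "as having at least one MRD negative result while on treatment", with a primary cut-off of 10^-5, and classes subjects with no negative result, including those untested or with missing samples, as positive. SAP 5.8 states: "The on-treatment period begins on the date of the first dose of trial medication". SAP 5.2.2 takes the last value before the first dose as baseline.

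**The concern.** An MRD-negativity rate is read as a measure of depth of remission: how often treatment takes detectable disease below the assay's limit. That reading needs disease that was detectable in the same compartment at the start. The clone is identified in the tumor biopsy and/or marrow aspirate (section 9.2.2.3) and then tracked in blood. It can therefore be known from tissue and yet be absent from blood before any treatment.

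Under 11.8.6 such a subject is a success whatever happens to the nodal disease, and a non-responder can count. The rate then mixes subjects cleared by treatment with subjects who had nothing to clear in blood. Their duration of MRD negativity does not measure a treatment effect either. In the SAP the same MRD status may also stratify PFS (10.2.3) and is used to split OS (10.2.5), so misclassification would carry into those summaries.

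**Working it through.** **Can a Cycle 1 Day 1 sample count?** Set the texts side by side.

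- Protocol 11.8.6 counts any sample, and Tables 13 and 14 both schedule one on Cycle 1 Day 1.
- Protocol 9.2.2.3 describes the blood samples as taken once treatment has started. That points the other way, but the restriction does not appear in 11.8.6.
- The SAP's on-treatment period is defined by calendar date, so a pre-dose sample on Day 1 falls inside it. The SAP's baseline rule makes that same sample the baseline. One sample is therefore both baseline and on-treatment.

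The Day 1 sample is thus included by omission, and the SAP does not settle the matter.

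**Would dropping Day 1 be enough?** No. No text requires a positive baseline. A subject negative at Day 1 who reads negative again at Cycle 2 Day 1, or at any later sample, still scores.

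**Size.** The documents give no MRD rate, no baseline-negative fraction and no target, so there is no figure to reproduce. Let b be the fraction MRD-negative in blood at baseline and r the fraction of baseline-positive subjects cleared by treatment. Both are assumed. Then

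- rate under 11.8.6 = b + (1 − b)r
- conversion rate among baseline-positive subjects = r
- conversion rate over the full analysis set (FAS) = (1 − b)r

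The first formula is exact if the Day 1 sample counts. If it does not, it also needs each baseline-negative subject to give at least one later negative.

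With n = 20 and no clearance (r = 0), the 11.8.6 rate is b:

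- b = 10%: 20 × 0.10 = 2 subjects
- b = 25%: 20 × 0.25 = 5 subjects
- b = 40%: 20 × 0.40 = 8 subjects

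With r = 30%:

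| b | Rate under 11.8.6 | Baseline-positive n | Rate among them | Conversion over FAS |
|---|---|---|---|---|
| 10% | 0.10 + 0.90 × 0.30 = 37.0% | 18 | 30% | 0.90 × 0.30 = 27.0% |
| 25% | 0.25 + 0.75 × 0.30 = 47.5% | 15 | 30% | 0.75 × 0.30 = 22.5% |
| 40% | 0.40 + 0.60 × 0.30 = 58.0% | 12 | 30% | 0.60 × 0.30 = 18.0% |

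The same drug effect gives reported rates from 37% to 58%, depending only on who was already negative at entry.

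**The case against.** The best defence is that the intended reading is narrower than 11.8.6. Section 9.2.2.3 ties blood MRD to the time after treatment starts, to response assessments and to CR. SAP 5.2.4 ties it to radiological assessments and to treatment, and Cycle 1 Day 1 is not an imaging timepoint. SAP 10.2.7 also summarises MRD by cycle and among complete responders, and 10.2.8 adds sustained negativity. A non-responder cannot enter the CR-restricted summaries. The endpoint is secondary, the cohort's primary endpoint is CR rate, and no hypothesis is tested.

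Much of this stands as context. It does not remove the defect: a post-treatment reading still lets a baseline-negative subject score later, and the extra summaries sit beside the overall FAS rate without replacing it. The SAP also does not cover the combination cohort.

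A reader might infer several stronger things that the documents do not support:

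- That the plan expressly counts a pre-dose sample. It does so only by omission. Explicit pre-dose timing applies to the Table 13 plasma sample and not to Table 14 whole blood.
- That exclusion 5 makes these subjects MRD-negative at entry. It concerns a high lymphocyte count or abnormal cells in blood. It makes baseline negativity plausible in lymphoma but does not establish it at 10^-5 or in plasma. It gives no support for CLL, where subjects may enter on circulating B lymphocytes.
- That the overall bias can only be upward. The baseline-negative mechanism acts upward, but the SAP counts untested or missing subjects as positive, which lowers the rate.
- That the inflation is 10% to 40%. Those are inputs, returned unchanged when r = 0.

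**Conclusion.** The concern holds for the combination DLBCL cohort. As written, the secondary MRD endpoint can be met by a subject who was never MRD-positive in blood and never responded, and the duration for that subject could start at baseline. This follows from the text and needs no assumption about numbers.

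The amount of inflation cannot be derived from the documents. It is b when treatment clears no one and (1 − r)b above the true clearance rate otherwise, since b + (1 − b)r − r = b(1 − r). This assumes that every baseline-negative subject has at least one counted negative sample, and it sets aside subjects with no evaluable result. The primary endpoint is unaffected, and no decision rule in the documents depends on MRD. The definition is nevertheless worth correcting before analysis, because the rate will be read as depth of remission.

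**What to change.** In protocol 11.8.6, and in SAP 5.2.4 and 10.2.7 once the SAP is updated to cover the combination cohort:

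- Count a subject as converting to MRD negativity only with a trackable clone, a positive pre-dose Cycle 1 Day 1 sample, and at least one negative sample after the first dose.
- Report the rate over baseline-positive subjects and also over the FAS. The second keeps the protocol's general rule that efficacy uses the FAS.
- Report separately how many subjects were negative at baseline, untrackable, or missing a result.
- Start the duration at the first negative sample after dosing.
- In Table 14, and in Table 9 for consistency, state that the Cycle 1 whole-blood MRD sample is taken pre-dose, in place of Day 1 with a +2 day window.

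The cost is mainly wording, since the Cycle 1 sample is already scheduled. The downsides are a smaller main denominator (18, 15 or 12 of 20 in the cases above), hence a wider interval, and a rate that may look less favourable.

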9.2.2 Evaluations

Efficacy assessments will be conducted as specified in the visit assessment schedules (refer to [Table 2](#), [Table 3](#), [Table 5](#), [Table 6](#), [Table 10](#), and [Table 11](#) will include the following: imaging assessments (including hepatic involvement and splenic involvement [size by vertical: cranial to caudal]), bone marrow assessment (as applicable), physical exam including constitutional symptoms, ECOG performance status, MRD status, and other procedures as necessary. All efficacy assessments should be conducted throughout the trial until disease progression, the start of new anti-cancer therapy, death or withdrawal of consent from trial participation, whichever occurs first.

Response assessment for B-cell NHL will be according to revised response criteria ([Cheson et al., 2014](#)) (refer to [Appendix 7](#)) and for CLL according to the iwCLL ([Hallek et al., 2018](#)) (refer to [Appendix 8](#)).

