11.8.2 Duration of Response

DoR only applies to subjects whose best objective response is CR or PR and is defined as the number of days from the first documentation of objective tumor response (CR or PR) to the date of first PD or death.

DoR will be censored and summarized in the same way as PFS (section [11.8.4](#)). The detailed censoring rules are specified in the SAP.

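### Duration of MRD negativity in the combination cohort does not end at progression or death, and reads long if those subjects are censored

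*Protocol*

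**What the plan says.** Protocol section 3, Table 20, lists "Rate and duration of MRD negativity" among the secondary endpoints of the combination expansion in R/R DLBCL (N=20).

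Protocol 11.8.6 defines both parts. For the rate: "The rate of MRD-negativity is defined as the proportion of patients with at least 1 MRD-negative sample". For the duration: "Duration of MRD-negativity is defined as the number of days from the first documentation of MRD-negativity to the date of MRD status change". A parenthesis adds that the change is to anything other than negative. The section does not mention progression, death, new therapy, censoring or an estimator. CR is not required to enter.

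Protocol 9.2.2 counts MRD among the efficacy assessments ("ECOG performance status, MRD status, and other procedures as necessary") and says when they stop: "All efficacy assessments should be conducted throughout the trial until disease progression, the start of new anti-cancer therapy, death or withdrawal of consent".

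Table 14 schedules whole-blood MRD on Day 1 of Cycles 1, 2, 3, 5, 7 and 10, then 6-monthly from Cycle 13 for up to 3 years, with an extra sample at CR. In Table 13 the ctDNA/MRD plasma row has an entry for unscheduled visits but is blank at the treatment discontinuation visit.

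Duration of response is treated differently in section 11.8.2. It runs from "the first documentation of objective tumor response (CR or PR) to the date of first PD or death", and "DoR will be censored and summarized in the same way as PFS".

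The SAP (section 1.1) is written to protocol v4.0, Amendment 2, before Amendment 5 added the combination cohort. SAP 5.4 has no MRD duration variable. SAP 10.2.8 reports the proportions with negativity sustained for at least 6 and 12 months, without saying how progression or death counts. SAP 10.2.1 sets Kaplan-Meier as the method for duration of response and comparable time-to-event endpoints.

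**The concern.** Protocol 2.2.2 and 4.3.2 put forward deeper and more durable benefit as the hypothesis for the combination, and this endpoint is one of the measures of durability. Its only end event is a laboratory result, and the protocol stops collecting that result once the subject has clinically failed. Subjects whose remission ends in progression or death, rather than in a positive sample first, then have no defined end date.

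The analyst must do something with them. Censoring at the last negative sample treats a subject who has just failed as if the risk of losing MRD negativity continued unchanged. Leaving them out reports durability only in those who converted under observation. Either way, the figure does not describe how long subjects remained alive, progression-free and MRD-negative.

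**Working it through.** The plan states no median, event count or sample-size figure for this endpoint, so there is nothing to reproduce. The check has three parts.

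**1. Definitions side by side (Protocol section 11.8)**

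| Endpoint | Ends at progression? | Ends at death? | Censoring rule given? |
|---|---|---|---|
| DoR (11.8.2) | yes | yes | yes, as PFS |
| PFS (11.8.4) | yes | yes | yes |
| OS (11.8.5) | no | yes | yes |
| Duration of MRD negativity (11.8.6) | no | no | no |

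**2. Who can reach the end event**

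- Death while MRD-negative: no later sample is possible, so the event cannot occur.
- Progression while last MRD-negative: sampling stops under 9.2.2 and none is scheduled at discontinuation, so the event needs an unscheduled sample.

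**3. Size, for illustration only**

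All rates are assumed. Let m be the median time to MRD relapse and p the median time to progression or death, with independent exponential times, so the hazards are ln2/m and ln2/p.

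- Median with progression and death censored: ln2 / (ln2/m) = m
- Median with them as end events: ln2 / (ln2/m + ln2/p) = 1 / (1/m + 1/p)
- Share of durations that end in progression or death: (1/p) / (1/m + 1/p)

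| m, p (months) | Censored | As events | Share ending in progression or death |
|---|---|---|---|
| 12, 6 | 12 | 1/(1/12+1/6) = 4.0 | 2/3 |
| 12, 12 | 12 | 1/(1/12+1/12) = 6.0 | 1/2 |
| 24, 12 | 24 | 1/(1/24+1/12) = 8.0 | 2/3 |

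The probability of still counting as MRD-negative at 12 months is 2^(-12/median). It is 0.50 against 0.13, 0.50 against 0.25, and 0.71 against 0.35 in the three rows.

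MRD is not observed continuously, so the same rates were run through the Table 14 schedule. There were 20,000 simulated subjects per scenario, with the first negative sample at Cycle 3 Day 1, sampling stopped at progression or death, and subjects without an event censored at their last negative sample. Medians are in months.

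| m, p | No event as written | Censored vs as events | Same, if half of those without an event have a positive unscheduled sample at failure | Observed changes only |
|---|---|---|---|---|
| 12, 6 | 72% | 15.2 vs 4.1 | 6.4 vs 4.2 | 3.7 |
| 12, 12 | 55% | 15.2 vs 6.4 | 9.2 vs 6.4 | 6.4 |
| 24, 12 | 71% | 27.2 vs 8.9 | 13.9 vs 8.9 | 9.2 |

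Over all six combinations of m = 12 or 24 with p = 6, 12 or 24, between 38% and 83% of MRD-negative subjects have no event under the written definition. The upward shift comes from censoring. A median of observed changes only lies near the composite, but it leaves out the subjects in the second column.

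**The case against.** The strongest reply is that 11.8.6 is incomplete rather than biased. It names no estimator, and the protocol defers detail to a SAP. The only SAP available predates this cohort, so its Kaplan-Meier default was not written for this endpoint. Protocol 11.8.4 lets even PFS fall back to simple descriptive statistics when events are few, which is plausible with 20 subjects. Time to MRD conversion is also a legitimate quantity in its own right.

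Part of this stands. A reader might infer that the endpoint is biased long as it is written. The documents do not support that without the further step of censoring progression and death, and a summary of observed changes shows little upward shift. A reader might also infer that a subject who progresses can never record a change. That is strict only for death. Table 13 allows unscheduled sampling, section 9.2.3.2 lets subjects stay on trial until suspected progression is confirmed, and Day 1 of Cycles 7, 10 and 13 falls at Weeks 24, 36 and 48, when scans are due. A sample there may turn positive before progression is called.

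Independence is a convenience too. MRD tracks the malignant clone, so if positivity usually comes first and is sampled, fewer subjects fail while negative and the gap narrows.

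What does not stand is that nothing needs to change. Section 11.8.6 states a rule with one end event, the available SAP does not supply another, and the alternative to censoring omits the failures.

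**Conclusion.** The point holds in a conditional form. As defined, duration of MRD negativity gives no end date to subjects who die while MRD-negative, and usually none to those who progress while last MRD-negative. Under Kaplan-Meier censoring the result is too long. In the three illustrative cases the median is inflated threefold, twofold and threefold (12/4.0, 12/6.0, 24/8.0). The size rests wholly on assumed, independent exponential rates and shrinks if progressing subjects have unscheduled positive samples.

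It would go too far to say that a failing cohort would pass unnoticed. DoR, PFS and OS are secondary endpoints of the same cohort and all count death. The trial is descriptive, with no formal hypothesis, so what is affected is the interpretation of one secondary endpoint in about 20 subjects, not a test or a sample size. The definition should still be corrected before it is analysed.

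**What to change.** In Protocol 11.8.6, and in a SAP updated to Amendment 5:

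- Define the duration as time from the first MRD-negative sample to the earliest of an MRD-positive result, documented progression or death.
- Censor at the last MRD sample before data cut-off or the start of new anti-lymphoma therapy.
- Estimate by Kaplan-Meier, as for DoR.
- State the MRD cut-off (SAP 5.2.4 has 10^-5 as primary) and how indeterminate or missing samples count.
- If time to MRD conversion alone is of interest, keep it as a supplementary summary with progression and death as competing events.

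The cost is wording in two documents. No new samples or visits are needed. The reported duration becomes shorter, and it mixes molecular and clinical failure, which is why the supplementary summary is worth keeping.
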